Paediatric subjects for this study are classified as:

- Newborn infants (birth to 27 days. Pre-term newborn infants born \leq 37 weeks gestation will be included within the group)
- Infants and toddlers (28 days to <24 months)
- Children (2 to 11 years)
- Adolescents (12 to <18 years)

42 paediatric subjects with intra-operative cerebrospinal fluid (CSF) leak following primary suturing of the dura will be randomized in a 2:1 allocation ratio and will be stratified by surgical procedure, posterior fossa or supratentorial to either EVICEL® Fibrin Sealant (Human) or additional dural sutures.

Subjects will be followed post-operatively through discharge and for 30 days (\pm 3 days) post-surgery. The incidence of CSF leaks will be assessed within 5 days (\pm 2 days) and 30 days (\pm 3 days) post-operatively as detected by any of the following: clinical observation, diagnostic testing or the need for surgical intervention to treat a CSF leak or pseudomeningocele.

SUBJECTS RANDOMIZED TO EVICEL®

For subjects randomized to receive EVICEL® Fibrin Sealant (Human), a thin layer will be applied to the entire length of the suture line and the adjacent area to at least 5mm away, including all suture holes. If necessary, a second layer of EVICEL® may be applied. A cure time 1-2 minutes should be allotted between layers to allow for polymerization. CSF leakage will be evaluated with a Valsalva maneuver 20-25 cm H₂O for 5-10 seconds.

If CSF leakage is still apparent a second treatment (up to two layers) with EVICEL® may be applied. CSF leakage will be re-evaluated with a second Valsalva maneuver 20-25 cm H₂O for 5-10 seconds.

- If watertight closure is not evident after this final Valsalva maneuver, the subject will be deemed a failure and the surgeon may revert to his/her standard of care for closure including the use of other commercially available fibrin sealants (except EVICEL®) or an onlay dural patch.
- If watertight closure is achieved, no further treatment, including the use of onlays, will be allowed.

Closure of the remaining layers of the surgical site will be performed according to the surgeon's standard of practice.

SUBJECTS RANDOMIZED TO CONTROL

Subjects randomized to Control (Additional Sutures) will receive additional dural repair sutures applied immediately to the dural suture line after randomization as deemed necessary by the surgeon. CSF leakage will be evaluated with the Valsalva maneuver 20-25 cm H₂O for 5-10 seconds.

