3. OVERVIEW OF STUDY DESIGN

This is a prospective, randomized, open-label, multi-center controlled study evaluating the safety and effectiveness of EVICEL® as an adjunct to sutured dural closure compared to standard adjunctive dural closure techniques using additional repair sutures only to obtain an intraoperative watertight dural closure. Subjects will be screened and selected from the patient population of approximately 4-8 clinical sites.

Subjects will undergo an elective or urgent posterior fossa or supratentorial procedure (craniectomy or craniotomy). Upon completion of the primary sutured dural repair, the closure will be evaluated for intraoperative CSF leakage with a baseline Valsalva maneuver 20-25 cm H₂O for 5-10 seconds. If a spontaneous leak is apparent immediately after dural closure, no Valsalva will be performed. Subjects who have an identified CSF leak (spontaneous or as identified with the Valsalva) will be enrolled into the study.

Subjects will be randomized to either EVICEL® Fibrin Sealant (Human) or to adjunctive dural closure techniques using Additional Sutures only (Control) in a 2:1 allocation ratio and will be stratified by surgical procedure, posterior fossa or supratentorial.

Subjects will be followed post-operatively through discharge and for 30 days (± 3) post-surgery. The incidence of CSF leaks will be assessed within 5 days (± 2 days) and 30 days (± 3 days) post-operatively as detected by any of the following: clinical observation, diagnostic testing or the need for surgical intervention to treat a CSF leak or pseudomeningocele.

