7.2 Procedures for Handling Biological Samples

7.2.1 Laboratory Tests

All laboratory investigations will be performed at each local hospital laboratory. The volume of blood to be taken will be determined according to the standard practices of each hospital. The normal reference ranges and laboratory accreditation certificates must be provided to ETHICON.

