8.1 Sample Size Determination

The sample size required for the trial is 42 randomized Subjects. This sample size is considered adequate by EMA Paediatric Investigation Plan to summarize the data descriptively. The continuous data will be summarized by number of subjects, mean, median and standard deviation (SD).

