8.2 Primary effectiveness analysis

The primary effectiveness endpoint is the proportion of success (intraoperative watertight closure) in the treatment of intraoperative CSF leakage defined as no CSF leakage from dural repair intraoperatively, during a Valsalva maneuver 20-25 cm H₂O for 5-10 seconds.

No formal sample size calculation has been performed for this study. The sample size required for the trial is 42 randomized paediatrics subjects recruited from 6-8 sites within the European Union. This sample size is considered adequate by EMA Paediatric Investigation Plan to summarize the data descriptively.

The primary effectiveness endpoint will be analyzed using the FAS and the PP set. However, the primary analysis will be based on the FAS. The PP analysis will be considered confirmatory.

In all cases, treatment allocation will be based on randomization for the primary effectiveness endpoint using the FAS. If more than two subjects are mis-randomized, then an additional confirmatory analysis based on treatment received will be performed for the primary effectiveness endpoint, using the FAS.

The proportion of successes will be summarized descriptively by treatment group. In addition, a two-sided 95% confidence intervals (CIs) will be reported for the ratio of the proportion of success in the EVICEL group/proportion of success in Control group (P_E/P_C), using the Farrington-Manning score method.

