2.2.2	5-day (± 2 days) and 30-day (± 3 days) follow-up assessments – FAS	Indication of re-hospitalizations since previous study visit, indication of surgical procedures since previous study visit, indication of relevant changes in medical history since screening, presence of clinically significant changes to subject since baseline, surgical site assessment, including presence of infection (brain abscess, meningitis, and/or surgical site infection – superficial incisional, deep incisional and/or organ-space), hematoma (intradural, extradural, and/or subcutaneous), pseudomeningocele, and other surgical site experience, wound healing assessment, CSF leak determination - all (d)	G2
3	Safety data		
3.1	Adverse Events		
3.1.1	Number of subjects experiencing any during/post treatment AE by category – Safety analysis set		AS
3.1.2	Adverse events (during/post treatment) by subject, MedDRA preferred term and system organ class – Safety analysis set		AM
3.1.3	Summary of during/post treatment adverse events by subject and coded terms, preferred terms occurring in $\geq 5\%$ of subjects – Safety analysis set		AM
3.1.4	Summary of during/post treatment serious adverse events by subject and coded terms – Safety analysis set	Includes adverse events for which the answer for CRF question “Serious?” in the CRF is “Yes”	AM
3.1.5	Summary of during/post treatment surgical procedure related (possibly, definitely) adverse events by subject and coded terms – Safety analysis set	Includes adverse events for which the answer for CRF item “Relationship to surgical procedure” is “Possibly related” or “Related”.	AM
3.1.6	Summary of during/post treatment study treatment related (possibly, definitely) adverse events by patient and coded terms – Safety analysis set	Includes adverse events for which the answer for CRF item “Relationship to study treatment” is “Possibly related” or “Related”.	AM

No	Title of table/figure	Notes	Shell ¹
3.2	Laboratory data	Reported in SI units	
3.2.1	Laboratory data: Complete Blood Count - Safety analysis set	At baseline and at 5-day follow-up	L
3.2.2	Laboratory data: White Blood Cell Differential - Safety analysis set	At baseline and at 5-day follow-up	L
3.2.3	Laboratory data: Creatinine, Liver Function Test and Electrolytes - Safety analysis set	At baseline and at 5-day follow-up	L
3.3	Other safety data		

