APPENDIX 1 - Notes on Shell Tables

These are meant to represent the **style** of tables, slight differences in the CRF will result in more/less rows in the tables or more/less categories for a parameter. Items to note are highlighted in green.

Single arm studies will only have one column of data (unless specific comparisons detailed in SAP).

Treatment labels will be as defined in section 7.1.

Footnotes will change according to the requirements of the study.

EXAMPLE TABLE AM (Adverse Event MedDRA summary)	2
EXAMPLE TABLE AS (Adverse Event Overall Summary)	3
EXAMPLE TABLE DC (Discrete data- change)	4
EXAMPLE TABLE DG (Demographics)	5
EXAMPLE TABLE DS (Disposition of subjects)	6
EXAMPLE TABLE E (Enrollment)	7
EXAMPLE TABLE G1 (General table 1, with total)	8
EXAMPLE TABLE G2 (General table 2, without total)	9
EXAMPLE TABLE G3 (General table 3, with stats comparison)	10
EXAMPLE TABLE HX (Physical exam / medical / surgical history)	11
EXAMPLE TABLE L (Laboratory results)	12
EXAMPLE TABLE PD (Protocol deviations)	13
EXAMPLE TABLE ST (Analysis sets)	14

EXAMPLE TABLE AM (Adverse Event MedDRA summary)

Table 14.3.1.x
 <<Title as SAP>> ^
 Safety analysis set

System organ class	Preferred term	Ethicon trt (n=99)	Comparator (n=99)	Total (n=999)
BLOOD AND LYMPHATIC SYSTEM DISORDERS	Total	9 (9.9%)	9 (9.9%)	9 (9.9%)
	ANAEMIA	9 (9.9%)	9 (9.9%)	9 (9.9%)
CARDIAC DISORDERS	Total	9 (9.9%)	9 (99.9%)	99 (9.9%)
	ACUTE MYOCARDIAL INFARCTION	9 (9.9%)	9 (9.9%)	9 (9.9%)
	ANGINA PECTORIS	9 (9.9%)	9 (9.9%)	9 (9.9%)
	ATRIAL FIBRILLATION	9 (9.9%)	9 (9.9%)	9 (9.9%)
	ATRIOVENTRICULAR BLOCK	9 (9.9%)	9 (9.9%)	9 (9.9%)
	COMPLETE			
	CARDIAC ARREST	9 (9.9%)	9 (9.9%)	9 (9.9%)
	CARDIAC FAILURE	9 (9.9%)	9 (9.9%)	9 (9.9%)
	CARDIAC FAILURE CONGESTIVE	9 (9.9%)	9 (9.9%)	9 (9.9%)
	MITRAL VALVE INCOMPETENCE	9 (9.9%)	9 (9.9%)	9 (9.9%)
	MYOCARDIAL INFARCTION	9 (9.9%)	9 (9.9%)	9 (9.9%)
	SINUS BRADYCARDIA	9 (9.9%)	9 (9.9%)	9 (9.9%)
	SUPRAVENTRICULAR TACHYCARDIA	9 (9.9%)	9 (9.9%)	9 (9.9%)
	TACHYCARDIA	9 (9.9%)	9 (9.9%)	9 (9.9%)
	VENTRICULAR TACHYCARDIA	9 (9.9%)	9 (9.9%)	9 (9.9%)
ENDOCRINE DISORDERS	Total	9 (9.9%)	9 (9.9%)	9 (9.9%)
	ADRENAL MASS	9 (9.9%)	9 (9.9%)	9 (9.9%)
GASTROINTESTINAL DISORDERS	Total	99 (99.9%)	99 (99.9%)	99 (99.9%)
	ABDOMINAL DISTENSION	9 (9.9%)	9 (9.9%)	9 (9.9%)
	ABDOMINAL HAEMATOMA	9 (9.9%)	9 (9.9%)	9 (9.9%)
	ABDOMINAL PAIN	9 (9.9%)	9 (9.9%)	9 (9.9%)
	ACUTE ABDOMEN	9 (9.9%)	9 (9.9%)	9 (9.9%)
	CONSTIPATION	9 (9.9%)	9 (9.9%)	9 (9.9%)
	DIARRHOEA	9 (9.9%)	9 (9.9%)	9 (9.9%)

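### The SAP plans laboratory summary tables that Protocol 8.4.2 and SAP 9.4 exclude, and no planned output uses the collected reference ranges to count children whose values became abnormal

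*SAP*

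**What the plan says.** **Population and setting.** The Protocol Synopsis defines four age groups, starting with "Newborn infants (birth to 27 days", which includes pre-term infants, then "Infants and toddlers (28 days to <24 months", then children, then adolescents under 18. Forty-two children are to be randomised at about 4 to 8 sites (SAP 8.2 gives 6 to 8). Protocol 3 describes the allocation as "in a 2:1 allocation ratio and will be stratified by surgical procedure, posterior fossa or supratentorial". Age is not a stratification factor. Under Protocol 7.2.1 each site uses its own hospital laboratory, and "The normal reference ranges and laboratory accreditation certificates must be provided to ETHICON".

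**Planned outputs.** SAP 10.2.2 assigns shell L to Tables 14.3.2.1 (blood count), 14.3.2.2 (white cell differential) and 14.3.2.3, titled "Laboratory data: Creatinine, Liver Function Test and Electrolytes - Safety analysis set". Shell L gives mean with SD, median with range, number with missing, and the 95% CI of the mean, by arm. It does so for three blocks per analyte: screening, post-operative and difference. Nothing is split by age or laboratory. Listings 16.2.7.2.1 to 16.2.7.2.3 give individual results at baseline and day 5. Appendix 1 also contains a baseline-by-visit shift layout, "EXAMPLE TABLE DC (Discrete data- change", but no table in SAP 10.2.2 is assigned to it.

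**Text rules.** Protocol 8.4.2 says laboratory values and changes are listed and not summarised, and sends clinically significant changes to the adverse event summary. SAP 9.4 repeats the list-only rule, run into a sentence about adverse events, but omits the statement about clinically significant changes.

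**The concern.** There are two problems. First, the text and the table list disagree on whether laboratory data are summarised at all, so a programmer following one will breach the other.

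Second, in a paediatric safety study the useful laboratory question is whether a child moved from normal to abnormal after treatment. What is normal for analytes such as creatinine or blood counts depends on the child's age (general clinical knowledge, not stated in the documents), and limits can also differ between hospital laboratories. The by-visit rows mix all of this together. The ranges that would sort it out reach the sponsor but feed into no specified output.

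At stake is the readability of the laboratory safety data in the first paediatric use of the product described here. A handful of children with new abnormalities could appear only as an unremarkable mean and a wide range. Someone would have to find them by reading listings, or rely on a judgement of clinical significance that has no written criterion and may be made knowing the arm.

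**Working it through.** **1. Nothing to reproduce.** SAP 8.2 states: "No formal sample size calculation has been performed for this study". No laboratory means, SDs or expected effects are given. The only check available is the split: 42 × 2/3 = 28 EVICEL and 42 × 1/3 = 14 Control.

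**2. Summarised or not?**

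| Place | Instruction for laboratory data |
|---|---|
| Protocol 8.4.1 | Laboratory tests are among the items summarised on the Safety Set |
| Protocol 8.4.2 | Values and changes listed, not summarised |
| SAP 8.4 | Day-5 laboratory data summarised descriptively |
| SAP 9.4 | All safety variables summarised descriptively; then values and changes listed, not summarised |
| SAP 10.2.2, shell L | Values and changes summarised by arm |

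The conflict is therefore also inside each document, not only between them.

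**3. Are the reference ranges used?** SAP 9.2, 9.4, the notes to Tables 14.3.2.1 to 14.3.2.3, the notes to Listings 16.2.7.2.1 to 16.2.7.2.3 and shell L mention no limit, flag or out-of-range count. A note under shell L says discrete laboratory data are summarised just by visit unless the SAP specifies otherwise, so a shift display will not appear by default.

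**4. By-visit rows.** Let D be the gap in normal level between the youngest children and the rest, and p the share of youngest children. Neither is in the documents; p = 0.25 is assumed, with range 0.10 to 0.40.
- Within-arm SD from age mix alone = D√(p(1−p)) = 0.43D (0.30D to 0.49D).
- SD of the chance arm difference in means = D√(p(1−p)(1/28 + 1/14)) = 0.14D (0.10D to 0.16D).

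The chance that an age group's share differs by 20 percentage points or more between arms (exact hypergeometric, 28:14) is 0.9% if the group has 4 of the 42 children, 9% if 8, 17% if 14 and 33% if 21.

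**5. Difference rows.** If a child's offset a is constant, (a + y₁) − (a + y₀) = y₁ − y₀, so both D-based figures in step 4 fall to zero. An effect proportional to level would remain in part.

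What these rows do not do is count abnormal children. One EVICEL child whose value doubles from the average moves the mean change by 1/28 = 3.6% of the average. With visit-to-visit noise v (assumed, as a fraction of the average), the standard error of that arm's mean change is v√2/√28:
- v = 10%: 2.7%
- v = 15%: 4.0%
- v = 20%: 5.3%

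The shift is below one standard error once v exceeds 1/√(2 × 28) = 13.4%. The printed range may show the extreme change, but not whether the value is abnormal for that child.

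**6. Does age mix bias the comparison?** A simulation of 40,000 re-randomisations assumed an age split of 2/10/18/12, 15% visit noise and no treatment effect.

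| Normal level, youngest to oldest | Age share of raw variance | SD of arm difference, raw (% of mean) | SD of arm difference, change (% of mean) |
|---|---|---|---|
| Doubles | 56% | 7.6 | 7.1 |
| Triples | 71% | 9.5 | 7.1 |

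The mean arm difference was about zero throughout: age mix adds noise, not systematic bias.

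**The case against.** The strongest reply is that shell L already reports within-child change, with its range, by arm, and that the listings give every value at both visits. SAP 10.3 says all non-administrative database fields are listed, so if the CRF captures ranges or flags they would appear; the CRF is not available to check. Abnormal results also have other routes: the adverse event summary under Protocol 8.4.2, and the item on clinically significant changes since baseline in Table 14.2.2.2. If the list-only rule prevails, the pooled tables disappear altogether. The unused shift shell is weak evidence, because Appendix 1 is a generic style set and shell G3 is unassigned too. Finally, the study is descriptive by design; Protocol 8.1 says of the 42 subjects: "This sample size is considered adequate by EMA Paediatric Investigation Plan to summarize the data descriptively".

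Much of this stands. A reader might infer that the tables reflect age mix more than any treatment effect. The documents do not support that: they give no value for D, no age split and no expected effect, the expected imbalance under randomisation is zero, and the Difference rows cancel constant offsets. A reader might also infer that an abnormality surfaces only if an unblinded investigator reports it. That is wrong too, because individual listings exist.

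The objection does not supply a count by arm of children who became abnormal. The clinical-significance routes state no criterion, and the item in Table 14.2.2.2 is not specific to laboratory results. If the tables are dropped, the listings still specify no out-of-range flag.

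**Conclusion.** The point holds in two parts. The contradiction over summarising laboratory data is plain on the page and must be resolved. Separately, no planned table, listing note or cut-off uses the reference ranges, so normal-to-abnormal shifts are not counted by arm whichever way the contradiction is settled.

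The size is modest. The age-mix figures apply only to the by-visit rows and are expressed in an unknown D with an assumed p. The single-child comparison rests on assumed visit noise: at 15% the shift is just under one standard error, at 10% it is about 1.3 (3.6/2.7). None of this shows that the tables would mislead about a treatment effect; it shows that they do not answer whether children became abnormal. The age-dependence of normal values is general knowledge. The primary endpoint is unaffected.

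**What to change.** - Reconcile Protocol 8.4.1 and 8.4.2 with SAP 8.4, 9.4 and 10.2.2, stating once whether laboratory data are summarised, and separate the laboratory text in SAP 9.4 from the adverse event sentence.
- In SAP 9.2 and 9.4, classify each value as low, normal or high against the local laboratory's range for the child's age. Protocol 7.2.1 does not say the supplied ranges are age-specific, so ask sites for age-specific ranges where they have not sent them.
- Present baseline-to-day-5 shift counts by arm using shell DC. Keep any raw means as supportive only.
- Flag out-of-range values in Listings 16.2.7.2.1 to 16.2.7.2.3. This is needed even if all summary tables are removed.

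The cost is SAP wording, programming, entry of the ranges and possibly a further request to sites. No new samples are needed. The downside is modest extra data-management work.

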10.3 Listings

Listings will be presented in centre, subject and visit order. The listings will be produced using the data from all subjects.

The columns indicate the listings that will be included in the report. All data available on the database, with the exception of fields used for administration, e.g. signature fields, will be included in the listing for the report.

Missing data will be shown by a space.

10.3.1 Appendix 16.2 listings:

All listings will be prefixed with 16.2.

No	Title of listing	Notes	CRF Page
1	Disposition of subjects		
1.1	Disposition of subjects	Includes reason for withdrawal and time to withdrawal	54
1.2	Visit dates	Includes informed consent and discharge details Includes derived data: -Nights in hospital -Days from procedure	Various
2	Protocol deviations		
2	Protocol deviations		50 and 52
3	Subjects excluded from the analysis		
3	Definition of analysis sets	As defined in Section 5 of this SAP	

No	Title of listing	Notes	CRF Page
4	Baseline characteristics		
4.1	Demographics, special histories, smoking status, and subject eligibility		8 and 10
4.2	Physical exam / medical / surgical history		12, 14, and 16
4.3	Inclusion and exclusion criteria		5
4.4	Concomitant medications	Derived data: -Days from procedure to start -Duration of Con Med	46 and 48
5	Surgical details		
5.1	Surgical procedure - re-operative information, timings including operation room and length of procedure, initial CSF leak determination, and randomization data	Includes derived data: -Time in the operating room -Length of procedure	18, 20, and 22
5.2	Surgical procedure – EVICEL application details		24 and 25
5.3	Surgical procedure – EVICEL application summary		25
5.4	Surgical procedure - Additional Sutures treatment details		28
5.5	Surgical procedure – Standard of Care methods for rescue therapy		30 and 31
6	Effectiveness data		
6.1	Effectiveness - primary effectiveness endpoint		
6.1	Primary effectiveness endpoint - Success (no CSF leak preoperatively during Valsalva maneuver) - FAS (sensitivity analysis) and PP set	Includes derived data: For ITT, missing data considered as: -Analysis#1 (primary): failures (d) Sensitivity analysis - missing data considered as: -Analysis#2: successes (d); -Analysis#3: failures for EVICEL and successes for Control (d)	
6.2	Follow-up assessments		
6.2.1	Post-surgery to hospital discharge assessment – length of hospital stay	Includes derived data: -Days from admission to discharge -Days from procedure to discharge	1
6.2.2	5-day (± 2 days) and 30-day (± 3 days) follow-up assessments		1 and 34
7	Safety data		
7.1	Adverse event listings (each subject)		
7.1.1	Adverse events	Includes derived data: -Days from procedure to start -Duration of AE	40, 42 and 43
7.1.2	Adverse event comments		42

No	Title of listing	Notes	CRF Page
7.1.3	Adverse events (MedDRA codes)		40, 42 and 43
7.1.4	Serious adverse events		40, 42 and 43
7.2	Laboratory data		
7.2.1	Laboratory data - Complete Blood Count	At baseline and at 5-day follow-up	37
7.2.2	Laboratory data - White Blood Cell Differential	At baseline and at 5-day follow-up	37
7.2.3	Laboratory data – Creatinine, Liver Function Tests and Electrolytes	At baseline and at 5-day follow-up	37
7.3	Other safety data		
7.3	Safety/secondary endpoints	Includes derived data: -Incidence of CSF leakage within 5 days (± 2 days) post-operatively -Incidence of CSF leakage within 30 days (± 3 days) post-operatively -Incidence of surgical site infections (SSI) according to National Healthcare Safety Network (NHSN) criteria within 30 days (± 3 days) post-operatively (separately for any SSI, superficial incisional SSI, deep incisional SSI, and organ/space SSI)	24, 25, 28, and 34

